6.2.3 Dispensing

The IMD must be dispensed in accordance with the protocol. For each patient included, a treatment kit will be provided and contain enough medication for the whole treatment period.

During the randomisation visit (Day 1), the investigator responsible for IMD dispensation (other than the first ophthalmologist investigator) will open the treatment unit corresponding to the allocated treatment number. Patient numbers must be allocated in an ascending order using the next available consecutive number (to be recorded in the e-CRF). Then, the site team member will provide the patient with the treatment kit to be taken home.

During the whole investigation treatment period, the evaluating ophthalmologist investigator will remain masked to the IMD.

Two dispensations will be performed as follow:

- On Day 1: one box containing enough medication for the treatment period Day 1 to Day 35 will be provided to the patient;
- On Day 35: one box containing enough medication for the treatment period Day 35 to Day 84 will be provided to the patient.

The site team member will instruct patients on the method of instilling the doses.

Patients will be instructed to return unused IMD as well as empty/partially empty containers of used IMD.

A daily record of the IMD containers dispensed to the patient will be maintained by the site team in the Drug Accountability Form.

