6.6 IMD

6.6.1 Description of the exposure to the IMD

IMD will be administered by the patient every day for 84 ± 7 days, one drop in each eye 2 to 4 times daily into the lower conjunctival sac of each eye.

There will be two treatment groups:

- T2259;
- Reference product: Vismed® Multi (Appendix II)

A detailed description of T2259 is available in Section 2, page 21. Vismed® Multi is described below.

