Start of previous and concomitant treatments	If substr(CMSTDAT, 9, 2)="ND" then the day will be replaced by 01 (first day of the month) If substr(CMSTDAT, 6, 5)="ND/ND" then the month and the day will be replaced by 01/01 (first day of the year) Name of the created variable: CMSTDATimp	Start date of medications (imputed, n) Will be used only to determined type of treatment (previous, concomitant or post-study)	DDMMYY
End date of previous and	If substr(CMENDAT, 9, 2)="ND" then the day will be replaced by 28, 30 or 31, depending of the month (last day of the	End date of medication (imputed, n)	

concomitant treatments	
month)
 
If substr(CMENDAT, 6, 5)="ND/ND" then the month and the day will be replaced by "12/31" (last day of the year)
 
Name of the created variable: CMENDATimp
	Will be used only to determined type of treatment (previous, concomitant or post-study)	
Start date and End date of previous and concomitant treatments	If CMSTDT Ne . And CMENDT Ne . Then PCM_DUR=((CMENDT-CMSTDT)+1)/30.44 If CMONGO="Y" Then PCM_DUR=.	Duration of treatment (in months)	Numeric (8.1)
Start date and end date of previous and concomitant treatments	If CMSTDATimp Ne . And CMENDATimp Ne . Then PCM_DUR=((CMENDATimp - CMSTDATimp)+1)/30.44 If CMONGO="Y" Then PCM_DUR=.	Duration of treatment (in months, with imputed dates)	Numeric (8.1)
Date of Instillation at Day 1	DAKDATD1=Date of instillation at D1 (VISITNUM=2)	Date of treatment initiation	DDMMYY
Date of last instillation	DAKDATLAST=Max(DAKDT)	Date of last treatment dispensation	DDMMYY
Imputed start date and end date of previous and concomitant treatment and date of selection visit	
If CMENDAT_dat Ne . And DAKDATD1 Ne . And CMENDAT_dat<DAKDATD1 Then CMTYP=1
 
If CMSTDAT_dat Ne . And DAKDATLAST Ne . And CMSTDAT_dat>DAKDATLAST Then CMTYP=3
 
If CMENDAT_dat Ne . And DAKDATD1 Ne . And CMENDAT_dat>=DAKDATD1 Then CMTYP=2
 
In case of ongoing with start date available: If CMTYP=, And CMONGO="Y" And CMSTDAT_dat Ne . And CMSTDAT_dat<DAKDATLAST Then CMTYP=2
 
In case of no start date of medication: If CMSTDAT_dat=. And DAKDATD1 Ne . Then CMTYP=2
 
If no date of treatment initiation: If DAKDATD1=. Then CMTYP=.
	Type of medication (previous or concomitant)	1="Previous" 2="Concomitant" 3="Post-study"

	Medications without type will be reviewed during the BR Meeting		

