6.5 Previous, Concomitant and Post-Study Medications

Previous and concomitant medication will be described overall and by treatment group in the FAS and the PP, separately for ocular and non-ocular treatments.

Treatments have been coded using the WHO Drug Dictionary Enhanced (WHODrug: B3 Global 2018Q3)

Number and percentage of patients with at least one previous or concomitant treatment will be presented overall and by ATC classification level 2 and ATC classification level 4, according to the 3 observation periods:

- Previous treatments: Treatments ended before the first instillation of the IMD or the same day
- Post-study treatment: Treatments started after the last instillation of IMD or the same day
- Concomitant treatments: Treatments started between the first and last instillation of the IMD (or the same day) or treatments started before the first instillation of the IMD and ended after the first instillation of the IMD.

Note: Results will be provided by descending frequency (for ATC classification level 2 and ATC classification level 4 with level 2, for the whole population analysed)

The Individual data listing will present all CRF items and calculated variables as treatment duration and periods (previous, post-study or concomitant treatment).

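### The SAP 3.3 cut-off for post-study drugs appears to be the last dispensation, not the last instillation, and the ordering of its IF rules misclassifies further drugs, so the medication tables would depart from SAP 6.5

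*SAP*

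**What the plan says.** SAP 3.3 contains one row whose source column refers to the last instillation. Its formula is "DAKDATLAST=Max(DAKDT" (closing bracket cut here) and its label is "Date of last treatment dispensation". That variable then drives the medication type, CMTYP. A drug is post-study when "CMSTDAT_dat>DAKDATLAST Then CMTYP=3". A later, separate statement reads "If CMENDAT_dat Ne . And DAKDATD1 Ne . And CMENDAT_dat>=DAKDATD1 Then CMTYP=2", where 2 means concomitant. A further statement makes an ongoing drug concomitant only if its type is still missing and its start precedes DAKDATLAST. Another makes any drug without a start date concomitant. Drugs left without a type go to blind review.

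SAP 6.5 defines the same three periods by the first and last instillation. For post-study it says "Post-study treatment: Treatments started after the last instillation of IMD or the same day".

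On timing, Protocol 6.2.3 states "Two dispensations will be performed as follow", on Day 1 and Day 35, the second being: "On Day 35: one box containing enough medication for the treatment period Day 35 to Day 84 will be provided to the patient". Protocol 6.6.1 states "IMD will be administered by the patient every day for 84 ± 7 days".

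**The concern.** Source and label in the SAP 3.3 row name two different events. Under the protocol those events are about seven weeks apart: the last box is handed out at Day 35 and the last drop is taken around Day 84. If the label is right, the second treatment period counts as after the study for any drug still being taken.

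The CMTYP statements are also written as independent IFs with no ELSE, so a later statement can overwrite a correct earlier one.

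What is at stake is the description of medication use. Ocular medication other than the authorised devices is prohibited from Day 1 to Day 84 (Protocol Table 1; SAP 2.2.2). A reader of the Day 84 secondary results would look to the concomitant tables for such drugs. Those started in the second period and continued would instead be in the post-study tables.

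**Working it through.** The documents give no figure to reproduce, so the check is a trace of the rules.

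**Inputs**
- Dispensations: Day 1 and Day 35, with a visit window of ± 3 days (Protocol 6.2.3 and 6.4.4).
- Dosing: 84 ± 7 days (Protocol 6.6.1).
- Classification rules (SAP 3.3) and period definitions (SAP 6.5).

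**CMTYP rules in written order**
1. End date known and before the first instillation: previous.
2. Start date known and after DAKDATLAST: post-study.
3. End date known and on or after the first instillation: concomitant.
4. Type still missing, drug ongoing, start before DAKDATLAST: concomitant.
5. Start date missing: concomitant.
6. First-instillation date missing: no type.

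**Trace**, first instillation Day 1, last instillation Day 84 (illustrative days)

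| Drug | DAKDATLAST = 35 | DAKDATLAST = 84 | SAP 6.5 |
|---|---|---|---|
| Start 10, ongoing | concomitant | concomitant | concomitant |
| Start 35, ongoing | no type | concomitant | concomitant |
| Start 36, ongoing | post-study | concomitant | concomitant |
| Start 60, ongoing | post-study | concomitant | concomitant |
| Start 84, ongoing | post-study | no type | both classes |
| Start 90, ongoing | post-study | post-study | post-study |
| Start 60, end 70 | concomitant | concomitant | concomitant |
| Start 90, end 100 | concomitant | concomitant | post-study |
| No start date, end before Day 1 | concomitant | concomitant | previous |

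**Date fault (depends on DAKDT).** For the ongoing drug started on Day 60, rule 2 gives post-study. Rule 3 cannot fire without an end date, and rule 4 cannot fire because a type is already set. Blind review does not pick it up, since it covers only drugs with no type. The ongoing drug started exactly on Day 35 has no type and does go to blind review. For a patient with only the Day 1 dispensation, DAKDATLAST is Day 1 and every ongoing drug started after Day 1 is coded post-study. That is wrong for all those started before that patient's last drop.

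**Order fault (independent of DAKDT).** For start 90 and end 100, rule 2 gives post-study and rule 3 overwrites it. For no start date and an end before Day 1, rule 1 gives previous and rule 5 overwrites it.

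**The faults interact.** The drug with start 60 and end 70 comes out right only because rule 3 overwrites rule 2. Turning the statements into an else-if chain while DAKDATLAST stays at Day 35 would make that drug post-study too. The date and the order have to be corrected together.

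**Length of the affected window**
- Nominal: 84 − 35 = 49 days; 49/84 = 58%.
- Shortest: 77 − 38 = 39 days; 39/77 = 51%.
- Longest: 91 − 32 = 59 days; 59/91 = 65%.

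**Same-day rules.** SAP 6.5 places a drug started on the day of the last instillation in both the concomitant and the post-study class. It also counts a drug that ended on the day of the first instillation as previous, whereas rule 3 makes it concomitant.

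**The case against.** The strongest reply is that no passage defines DAKDT. The row's source names the last instillation, the neighbouring row uses the same stem for the Day 1 instillation, and device returns are also recorded, so the field might hold a Day 84 date. If it does, the date fault disappears. This stands as a condition on that part. The label and the two-dispensation schedule still favour the Day 35 reading, the row contradicts itself either way, and the order fault does not depend on DAKDT.

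A reader might infer that prohibited drugs disappear from the report or escape the deviation review. The documents do not support that. The drugs move to Tables 3.5a and 3.5b, and by SAP 6.5 the individual listing carries all CRF items. Major deviations are decided at blind review (SAP 6.1.1), and no stated rule links CMTYP to the PP set.

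A reader might also infer that the primary comparison is confounded. The ongoing drugs coded post-study because of the Day 35 cut-off start after the Day 35 dispensation, and no analysis model in the SAP uses CMTYP. Nor does 58% mean that 58% of drugs are misclassified: it measures days, and no count of affected drugs is available.

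Finally, SAP Appendix 1 requires double programming of derived data. A second programmer who compared 3.3 with 6.5 could notice the mismatch. One who worked from 3.3 alone would reproduce it, so this is a possible safeguard and not a dependable one.

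**Conclusion.** The point holds in two parts.

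- **Conditional on DAKDT being the dispensation date:** ongoing drugs started after about Day 35 and before the last instillation are coded post-study instead of concomitant, over a window of nominally 49 of 84 days. With only the Day 1 dispensation, the window opens after Day 1.
- **Unconditional:** the rule order makes concomitant a drug started after the last instillation that has an end date, and a drug with no start date that ended before Day 1.

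Both contradict SAP 6.5. The effect is confined to descriptive Tables 3.1 to 3.5 and the period shown in Listing 4, and so to how the Day 84 secondary results are read. The Day 35 primary analysis and PP membership are not directly changed. It is worth correcting before database lock because the rule gives wrong tables as written and the correction is small.

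**What to change.** 1. Derive DAKDATLAST as the maximum ECENDT over the IMD records only (D1-D35 and D35-D84). Exclude the Hydrabak run-in records, which use the same variable in SAP 3.3. If no such date exists, use the end-of-study date. Correct the label to match.
2. Replace the CMTYP statements with one chain:
   - first-instillation date missing: no type, to blind review;
   - else end date non-missing and before the first instillation: previous;
   - else start date non-missing and after the last instillation: post-study;
   - else concomitant.
3. Keep the non-missing conditions, including the existing one on DAKDATLAST. SAS sorts a missing value below any date, so an unguarded end-date test would turn every ongoing drug into previous.
4. State one same-day rule for starts on the last-instillation day and endings on the first-instillation day, and use it in both 3.3 and 6.5. The chain above, with strict inequalities, makes both concomitant; if 6.5 is to keep another rule, change the inequalities to match.
5. Produce Tables 3.1 to 3.5 and the Listing 4 period from the revised rule.

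The cost is a few lines of derivation text and one sentence in 6.5. SAP 3.3 already uses all the dates needed, so there is no new data collection.

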4 SEQUENCE OF PLANNED ANALYSES

4.1 Interim analyses

No interim analysis is planned.

4.2 Final analyses and reporting

This SAP described the final statistical analysis.

The analyses will be performed after the database has been cleaned and locked.

A BR meeting will be conducted prior to database lock. Treatment allocations will not be un-blinded and no un-blinded analyses will begin until this SAP has been approved by the sponsor.

Any post-hoc exploratory analyses performed to provide support for planned analyses but not identified in this SAP will be documented and reported in appendices to the CSR and clearly identified as unplanned analyses in the text of the CSR.

4.3 Changes to statistical information in the clinical trial protocol

In the protocol, the final visit form can either be D84 visit or Withdrawal visit. Withdrawal visits specified in the final visit form will be reviewed during the BR meeting and reclassified to the closest missing planned timepoint (D8, D35 or D84).

Information collected during withdrawal visit will be used in the analysis as reclassified visit.

In the protocol, for the primary performance endpoint, the investigator site and the investigation product-by investigator site interaction was expected to be explored as a secondary analysis prior to presenting the final model. As the number of randomised patients by site is low, investigator site will not be tested but replaced by country effect.

For the primary performance endpoint, additional sensitivity analysis will be performed: Mixed Model for Repeated Measures (MMRM) model will be used including: treatment group, baseline value, visit, treatment group by visit interaction and treatment group by baseline value interaction.

To investigate the bias of recruitment before and after the recruitment interruption, patients will be classified without or with possible impact of COVID-19 pandemic based on their screening visit date respectively up to and including 18 MARS, or after the 18-MAR-2020. Descriptive analysis will be performed according to this variable (populations, countries, premature withdrawal, protocol deviations and demographic characteristics (age and sex). Moreover, for the primary endpoint, an exploratory model will be performed using initial model, adjusted on this new variable.

For the analysis of previous and concomitant medications, ATC level 2 and 4 will be used, instead of level 3 and 4 specified in the protocol.

For performance and tolerance assessment, Wilcoxon signed-rank test will be replaced by Cochran-Mantel-Haenszel (CMH) test, and Chi-2 test for Dry Eye Symptoms will be replaced by Cochran-Mantel-Haenszel (CMH) test.

In the safety endpoints, for the comparison between treatment group of the total score of the 6 predefined symptoms (unusual sensation upon instillation), Student T-test will be performed, instead of the use of Analysis of Covariance (ANCOVA) analysis as specified in the protocol. Student T-test will be performed if the normality of the data is verified. If the data have not normal distribution, Mann-Whitney Wilcoxon test will be used.

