2 STUDY DESIGN

2.1 Overview

This is a multicentre, randomised study, investigator-masked, 2 parallel groups (T2259 versus Vismed® Multi) of 38 evaluable patients each.

The patients were randomised after a run-in-period of 7 to 10 days with preservative free artificial tears (Hydrabak®, one drop in each eye 3 to 6 times daily). Then, they were treated with either T2259 or the reference product (Vismed® Multi) for 84 days (\pm 7 days).

Investigation visits were performed as following:

Day 1-10/Day 1-7	Selection visit (Visit 1)
Day 1	Randomisation/ Inclusion visit (Visit 2)
Day 8 (\pm 1)	Visit 3 Optional Visit (if the investigator and/or the patient thinks it is necessary)
Day 35 (\pm 3)	Visit 4
Day 84 (\pm 7)	Final visit (Visit 5)

The Visits V2, V3, V4 and V5 should have been performed at the same hour (± 4 hours).

Reclassification of visits:

All “premature withdrawal” visits will be reclassified as decided in BR Meeting. Number of days between premature withdrawal visits and randomisation visit will be calculated and depending of this number of days, visits will be reclassified to the nearest planned non-missing visit.

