6.2 Disposition of Patients

Descriptive statistics will be provided. No statistical test will be performed.

- Study dates: first date and last date will be provided for selection visit, inclusion visit and last visit (visit 5 or early withdrawal).
- Number and percentage of patients in each country and each site will be provided in FAS and Safety set.
- Status of patients:
 - Among all patients: number and percentage of patients selected and not selected, reason if not selected (as reported by the investigator at the selection visit)
 - Among selected patients: number and percentage of patients who attended inclusion visit, number and percentage of patients included and not included, reason if not included (as reported by the investigator on end-of-study page: Adverse event, lack of performance, withdrawal by subject, lost to follow-up, screen failure, other)
 - Among included patients: randomised (Yes, No)
 - Among randomised patients: number and percentage of patients with visits done (for each visit: Yes, No), visit type if Visit 5 done (Day 84 +/-7 days, Premature discontinuation visit), has the patient completed the study (Yes, No), reason if study not completed (Adverse event, lack of performance, withdrawal by subject, lost to follow-up, screen failure, other)

Non-selected patients, non-included patients and early withdrawals will be individually listed.

Note: In case of withdrawal, withdrawal visit will be re-assigned depending to the date of withdrawal. The withdrawal visit will be re-assigned to the closest planned missing visit (D8, D35 or D84). All re-assigned withdrawal visits will be discussed during BR and recorded in the BR meeting minutes.

- Analysis sets:
 - From randomised patients: Number and percentage in safety population, number and percentage of patients excluded from safety population and reason(s) for exclusion
 - From safety population: Number and percentage in FAS, number and percentage of patients excluded from FAS and reason(s) for exclusion
 - From FAS: Number and percentage in PP, number and percentage of patients excluded from PP and reason(s) for exclusion
 - Number and percentage of patients with major and minor protocol deviations, globally and for each section of deviation (inclusion criteria deviation, exclusion criteria deviation, randomisation, visit windows and chronology, run-in treatment compliance, IMD compliance, primary performance endpoint and secondary efficacy endpoints, other), in FAS.

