6.7 Performance analyses

6.7.1 Primary Performance Endpoint

Primary performance endpoint will be analysed only in the worst eye.

Descriptive tables will be produced presenting selection, baseline (D1), Day 8, Day 35 and Day 84 Oxford Total score and change from baseline for Oxford Total score at Day 8, Day 35 and Day 84.

Oxford grade at each visit and change from baseline at Day 8, Day 35 and Day 84 will be also described for each panel: temporal bulbar conjunctiva, corneal area and nasal bulbar conjunctiva.

The hypothesis of non-inferiority of T2259 compared to Vismed® Multi will be tested by calculating the bilateral 95% CI of the difference between groups (T2259 – Vismed® Multi) of the change from baseline of Oxford Total Score on Day 35. A two-way analysis of covariance (ANCOVA) model will be constructed using main effects of investigation product and baseline score as covariate. Adjusted means by investigation product will be presented as well as an estimate of the difference between adjusted means.

A 95% two-sided confidence interval, based on the ANCOVA model (2), will be computed for the difference of T2259 minus Vismed® Multi. If the upper bound is no higher than 2 points for the PP population, it will be concluded that the null hypothesis can be rejected and that T2259 is non-inferior to Vismed® Multi.

The result will be presented as follow:

Population	T2259 (N=XX)	Vismed® Multi (N=XX)	Difference T2259 – Vismed Multi	SE of Difference T2259 – Vismed Multi	95% CI
Day 1 (baseline) mean (SD)	X1	Y1			
Day 35 mean (SD)	X2	Y2			
Adjusted mean change (SE) between Day 1 and Day 35	[X2- X1]*(SE)	[Y2-Y1]*(SE)	[X2-X1] -[Y2-Y1]	SE	[Min - Max**]

* These values were expected as negative, meaning an improvement of the Oxford score.

** The upper bound indicates the maximal difference of change in disfavour of T2259.

This analysis will be performed firstly on the Per Protocol population on the observed data.

Same analysis will be performed on FAS population with imputation of values in case of missing data with LOCF technique (Day 8 or value in case of withdrawal) and without imputation (observed cases) for confirmation.

The country and the investigation product-by-country interaction will be explored as a secondary analysis prior to presenting the final model (1).

Same analysis as principal analysis (ANCOVA model) will be performed adjusted on possible impact of COVID-19 pandemic (3).

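### SAP 2.1 and SAP 4.3/6.2 give opposite rules for re-assigning withdrawal visits, and the 4.3/6.2 rule lacks a time-order and a tie condition and can fill Day 35 from well outside its window

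*SAP*

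**What the plan says.** Three places in the SAP describe what happens to a premature-withdrawal visit.

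- SAP 2.1 (reclassification of visits): "visits will be reclassified to the nearest planned non-missing visit".
- SAP 4.3 (changes from the protocol): these visits "will be reviewed during the BR meeting and reclassified to the closest missing planned timepoint (D8, D35 or D84".
- SAP 6.2 (disposition): "The withdrawal visit will be re-assigned to the closest planned missing visit (D8, D35 or D84".

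SAP 4.3 then settles how the value is used: "Information collected during withdrawal visit will be used in the analysis as reclassified visit". None of the three places gives a condition on time order, a rule for ties or a maximum distance from the target day.

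The control is blind review. SAP 6.2 states: "All re-assigned withdrawal visits will be discussed during BR and recorded in the BR meeting minutes". It also lists "visit windows and chronology" among the deviation sections. SAP 6.1.1 removes patients with major deviations from the per-protocol (PP) set.

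On the primary endpoint, SAP 6.7.1 says: "This analysis will be performed firstly on the Per Protocol population on the observed data". The FAS analysis follows "with LOCF technique (Day 8 or value in case of withdrawal) and without imputation (observed cases) for confirmation". The protocol (6.4.4) places Visit 4 at 35 ± 3 days after randomisation, and the Day 8 visit is optional (Protocol 6.4.3, SAP 2.1).

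**The concern.** The primary endpoint is the change in Oxford score at Day 35, so the rule that decides which values count as Day 35 helps define the primary dataset. Under any single definition of a missing visit, 2.1 and 4.3/6.2 choose their target from complementary sets. A programmer who works from 2.1 builds a different dataset from one who works from 4.3 or 6.2.

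Correcting 2.1 alone does not finish the matter. The 4.3/6.2 rule can place a value before a visit the patient has already made. It can also accept as Day 35 a value taken weeks before or after that day. Because SAP 4.3 uses the value as the reclassified visit, it is then analysed like an attended Day 35 visit in the FAS observed-case analysis and the MMRM, and in the PP analysis unless blind review takes the patient out.

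**Working it through.** **Inputs.** Targets are Days 8, 35 and 84 (SAP 4.3, 6.2). Days are elapsed days, visit date minus randomisation date, as in SAP 2.1, 3.3 and 6.2. The Day 35 window is 35 ± 3, so Days 32–38 (Protocol 6.4.4). There are 38 evaluable patients per arm, SD 2.5, margin 2, no true difference and one-sided alpha 2.5% (SAP 5.1). SAP 5.2 also has a study-day convention that adds one day; using it would move the boundaries by about one day.

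**The closest-missing rule (SAP 4.3/6.2), applied literally.** The boundaries are midpoints between the targets that are still missing: (8+35)/2 = 21.5, (35+84)/2 = 59.5, (8+84)/2 = 46.

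| Attended before withdrawal | Labelled Day 8 | Labelled Day 35 | Labelled Day 84 |
|---|---|---|---|
| Neither Day 8 nor Day 35 | up to 21 | 22–59 | from 60 |
| Day 8 only | – | 9–59 | from 60 |
| Day 35 only | 36–45 (46 is a tie) | – | from 47 |
| Day 8 and Day 35 | – | – | all |

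The third row is out of time order: a value taken after the attended Day 35 visit is filed as Day 8. It affects the Day 8 results and the MMRM, not the Day 35 ANCOVA.

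**Days accepted as Day 35, against Days 32–38.**

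- Day 8 attended: 59 − 9 + 1 = 51 days, of which 23 are before the window (9–31), 7 inside and 21 after (39–59).
- Day 8 not attended: 59 − 22 + 1 = 38 days, of which 10 are before (22–31), 7 inside and 21 after.

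These are counts of calendar days, not of patients. Days 39–59 arise only for a patient who missed Day 35 and still came to a later withdrawal visit.

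**The nearest-non-missing rule (SAP 2.1), applied literally.**

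- Day 8 only attended: every later withdrawal goes to Day 8, and the empty Day 35 stays empty.
- Day 35 attended: every later withdrawal goes to Day 35, a second Day 35 value with no rule for choosing between the two.
- No post-baseline visit attended: there is no post-baseline target.

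**Size per patient.** The plan's own figure first. SE = 2.5 × √(2/38) = 0.574. The non-centrality is 2/0.574 = 3.49 on 74 degrees of freedom, which gives power of 93.1%, so the stated minimum of 90% is met. The expected upper confidence limit is 1.99 × 0.574 = 1.14, which leaves 2 − 1.14 = 0.86 points to the margin.

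Assume that a re-assigned value lies 1 to 3 points from what Day 35 would have shown (the documents give no figure). One such patient moves an arm mean by 1/38 = 0.03 to 3/38 = 0.08 points. That is 1% to 4% of the margin, or 3% to 9% of the 0.86-point room. Using up that room at 3 points each would take 0.857/0.079 = 10.9, so 11 patients in one arm, all wrong in the same direction.

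**The case against.** Much of the case on the other side is sound.

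- **Drafting slip.** Two of the three places, including the section on changes from the protocol, use the missing-visit rule, and 2.1 gives unworkable results when read literally. A slip is the likely explanation. It still has to be corrected, because the text as it stands specifies a different dataset.
- **The Visit 5 form.** Withdrawal data are recorded on the final-visit form, so Day 84 could be called non-missing for a withdrawn patient, and some late withdrawals would then go to Day 84 under both rules. But 4.3 and 6.2 name Day 84 among the possible missing targets. The agreement appears only if missing is defined differently in different sections.
- **Blind review.** It precedes database lock (SAP 4.2), discusses and minutes every re-assignment, and could stop an out-of-order label. This is a real safeguard. It has no stated criterion, however: nothing makes an off-window re-assigned value a major deviation, and exclusion from PP does not change the FAS observed-case analysis.
- **Closest timepoint is a legitimate choice.** The rule is deterministic apart from one tie day. A narrow range would cost data, including treatment failures, and the FAS LOCF analysis already lets a withdrawal value stand in for Day 35 (Protocol 7.3.2). This stands, and it is why the range is better examined in a sensitivity analysis than imposed.

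Some stronger readings are tempting but not supported.

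- A reader might infer that SAP 4.3 contradicts 6.7.1 on what counts as observed. The two fit together: a value re-assigned to Day 35 is Day 35 data, and one re-assigned to Day 8 is available to LOCF.
- A reader might take the 101 randomised for about 76 PP-evaluable patients (SAP 5.1) as a measure of the problem. That gap covers every reason for non-evaluability and does not count re-assigned visits.
- A reader might object that a Day 15 withdrawal becomes Day 35 or Day 8 according to whether the optional visit took place. Any closest-missing rule has that property; it is not in itself an error.

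**Conclusion.** The point holds as a correction to make before unblinding. SAP 2.1 is wrong as written against 4.3 and 6.2. The shared 4.3/6.2 rule needs an order condition and a tie rule, and its reach into Day 35 (51 or 38 days accepted, 7 of them in window) should be made visible next to the primary result.

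The effect per patient is small: 0.03 to 0.08 points on an arm mean, given the assumed 1 to 3 point error and 38 per arm. Its direction is unknown, since withdrawals include treatment failures (Protocol 6.7.3) as well as other reasons. The number of re-assigned patients is not given. The documents therefore do not support a claim that the non-inferiority conclusion is biased or that its error rate is inflated by any particular amount; such a figure would rest on an invented share of re-assigned values.

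**What to change.** Before unblinding:

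1. In SAP 2.1, change non-missing to missing, so that 2.1, 4.3 and 6.2 state one rule. This also removes the second Day 35 values.
2. Add to that rule that no withdrawal visit is assigned to a timepoint earlier than a visit already attended, and add a tie rule. With targets 8, 35 and 84 the order condition alone sends Days 36–46 to Day 84 when Day 35 was attended. The tie clause covers any other day count or target.
3. Add one sensitivity analysis of the primary endpoint that leaves out re-assigned Day 35 values from outside Days 32–38, shown next to the PP and FAS observed-case results.

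The cost is a few lines of SAP text, a small change to the visit mapping and one extra table. In the sensitivity analysis only, a few patients are lost, possibly including treatment failures, so it should be read beside the main results and not in their place.
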